Jiao Tong University School of Medicine

Clinical Research Protocol

Project Name: Evaluation of the one-piece zirconia abutments and two-piece zirconia abutments with titanium bases for single implant crowns in esthetic region: a randomized split-mouth clinical trial with 1-year follow-up

Version Number: V 2.0

Version Date: 2020/12/10

Project Manager: [name]

Start and End Dates: 2020/12 – 2022/12

PROTOCOL TITLE:

Evaluation of the one-piece zirconia abutments and two-piece zirconia abutments with titanium bases for single implant crowns in esthetic region: a randomized split-mouth clinical trial with 1-year follow-up

Abstract

Objective: To evaluate the clinical, radiological and immunological outcomes of the one-piece zirconia abutments (OPZAs) and two-piece zirconia abutments (TPZAs) with friction-fitted titanium bases in single implant crowns in aesthetic region.

Materials and methods: The study is a single center, split-mouth and randomized controlled clinical trial. Eligible patients will be randomly assigned into two groups: OPZAs group (OG) and TPZAs group (TG). Survival rates, mechanical complication rates, bleeding on probing (BOP%), probing depth (PD), modified plaque index (mPI), marginal bone loss (MBL), concentrations of pro-inflammatory cytokines (TNF- α , IL-6) in peri-implant crevicular fluid (PICF), and pink esthetics score/white esthetics score (PES/ WES) will be evaluated.

Discussion: Results of the present study will help to evaluate the clinical, radiological and immunological outcomes of OPZAs and TPZAs with friction-fitted titanium bases in single implant crowns in aesthetic region and provide evidence for the effects of two types abutments on the health of peri-implant soft and hard tissue.

Keywords: zirconia abutment, one-piece, two-piece, peri-implant crvicular fluid, inflammatory factors, peri-implant diseases

1. Background

Dental implants have become a well-established contemporary clinical treatment with predictable long-term success in the rehabilitation of partially edentulous patients.¹⁻⁵ And in the area of its fixed supra-structure, metal-free materials offer an alternative to titanium-based restorations while ensuring high levels of biocompatibility and esthetics. The range of available materials was significantly expanded with rapidly evolving CAD/CAM technology. And this also provided access to materials classes and their combinations not previously available within conventional manufacturing, such as zirconia ceramics and hybrid ceramics.^{6,7}

With the increasing demand for esthetic restorations, attempts of using ceramic abutment had been made over the past 20 years because it can compensate for the unfavorable shade of titanium abutments.⁸⁻¹⁰ What's more, a study demonstrated that compared to titanium healing caps, zirconia ones had less bacterial adhesion.¹¹ Ceramic abutments are available in 2 main designs: one-piece(monolithic) zirconia implant abutment(OPZA) and two-piece hybrid zirconia abutment(TPZA).

The OPZAs has low fracture resistance and caused wear of implant fixtures,¹²⁻¹⁴ and TPZAs comprises a sleeve and a titanium insert. The zirconia sleeve, which can be prefabricated by using standardized procedures or customized by using computer-aided design and computer-aided manufacturing (CAD-CAM) methods, is resin bonded or friction fitted to a titanium insert.

The OPZAs were first introduced in 1993,^{15,16} intending to replace metal abutments and achieve higher esthetics in the anterior region. Shortly after that, the first experimental monolithic abutments made of partially stabilized zirconia were reported.^{17,18} Later, with the development of CAD/CAM technology, it has been possible to design individual abutment shapes. Subsequently,

the TPZAs were also widely used for avoiding direct contact between zirconia abutments and titanium implants.^{12,19,20}

To date, reports on the clinical performance of ZAs remain controversial. Different abutment type seems to be associated with different risks, which can arise at any stage of therapy and greatly influence patient's satisfaction and quality of life. Although some clinical investigations affirmed excellent performance of ZAs with survival rate approaching 100%,^{21,22} unexpected and early catastrophic fractures of OPZAs and TPZAs with friction-fitted titanium inserts both have been reported.^{22,23} OPZAs were considered to be accompanied by higher risks of fracture, screw loosening and permanent damage due to stress concentrations, especially with internal implant connections. While TPZAs with friction-fitted titanium inserts seem to require higher machining accuracy and failure of the connection between the zirconia sleeve and titanium insert is a concern.^{21,24-26}

Even though technological progress in the field of metal-free materials has given rise to considerable improvements of these two types of abutment over the decades, there is still lack of clinical evidence for the use of two types ZAs.

Recent studies also showed that pro-inflammatory cytokines in peri-implant crevicular fluid (PICF) were significantly related to peri-implant diseases and further marginal bone loss.^{27,28} Tumor necrosis factor alpha (TNF- α) and interleukin-6 (IL-6) are pro-inflammatory cytokines that appear to have an important role in periodontal tissue destruction.^{29,30} It's necessary to quantitatively determine the concentrations of cytokines in PICF of OPZAs and TPZAs with friction-fitted titanium inserts as potential biomarkers for peri-implant disease diagnosis.

Thus, the investigators designed this randomized split-mouth clinical trial to evaluate the

clinical, radiological and immunological outcomes of OPZAs and TPZAs with friction-fitted titanium inserts in single implant crowns in aesthetic region. The primary outcome is prespecified as mechanical complication rates at 1-year follow-up.

2. OBJECTIVES AND HYPOTHESIS

The purpose of the present study is to evaluate the clinical, radiological and immunological outcomes of the OPZAs and TPZAs with friction-fitted titanium bases in single implant crowns in aesthetic region. Survival rates, mechanical complication rates, bleeding on probing (BOP%), probing depth (PD), modified plaque index (mPI), marginal bone loss (MBL), concentrations of pro-inflammatory cytokines (TNF- α , IL-6) in peri-implant crevicular fluid (PICF), and pink esthetics score/white esthetics score (PES/ WES) will be included in the comparison indicators. The null hypothesis is that there is no significant difference regarding mechanical complication rates between two groups.

2. METHOD/DESIGN

Overview

The present study is designed as a prospective, single-center, split-mouth, randomized controlled clinical trial. The investigators plan to recruit several adult patients who have two missing teeth in the maxillary anterior region and plan to be restored with two single implant crowns. The clinical component of the study will be initiated in Feb. 2019 at the Department of Oral and Maxillo-facial Implantology, Shanghai Ninth People's Hospital, Shanghai Jiao Tong University, China.

All patients received oral hygiene instruction and periodontal treatment before implant surgery.

The investigators will record the age, gender, physical health of all participants and they will meet the following inclusion criteria. Peri-apical radiographs with paralleling technique will be performed on the day of final restorations delivery. Clinical radiological and immunological re-evaluations will be performed at 1 year after the final crowns delivery.

Inclusion criteria

1) age \geq 18; 2) patients with two missing teeth in esthetic region and plan to be restored with two single implant crowns; 3) adjacent to natural teeth; 4) absence of oral mucosal disease and oral infection; 5) implants with conical connection (Nobel Active, Nobel Biocare® or NobelReplace Conical Connection, Nobel Biocare®); 6) patients with the willingness to participate in the present study.

Exclusion criteria

1)Heavy smokers (>10 cigarettes/day); 2) uncontrolled periodontitis (Full mouth plaque score $>20\%$, full mouth bleeding score $>25\%$, residual pocket depth $>5\text{mm}$); 3) with systematic diseases that may affect implant therapy, such as uncontrolled diabetes mellitus (Fasting blood-glucose $>7.2\text{mmol/L}$, Glycosylated hemoglobin $>7\%$), current intake of bisphosphonates (treatment for malignancy), pregnant(or plan to get pregnant), with history of radiation therapy in head and neck region.

Recruitment

Patients who have two missing teeth in the maxillary anterior region and plan to be restored

with two single implant crowns will be recruited at the Department of Oral and Maxillo-facial Implantology, Shanghai Ninth People's Hospital, Shanghai Jiao Tong University, China. Eligible patients will receive the study information and informed consent, and any patients who do not sign the consent will not be included in the study.

Allocation and blinding

Eligible patients have two missing teeth, and they will be randomly assigned into two groups: OPZAs group (OG): restored with the OPZAs; TPZAs group (TG): restored with the TPZAs with friction-fitted titanium bases. The study is an open-label trial without blinding.

Outcomes

All the included patients will be recalled for clinical, radiological and immunological re-evaluations 1-year after the final crowns delivery. Survival rates, mechanical complication rates, bleeding on probing (BOP%), probing depth (PD), modified plaque index (mPI), marginal bone loss (MBL), concentrations of pro-inflammatory cytokines (TNF- α , IL-6) in peri-implant crevicular fluid (PICF), and pink esthetics score/white esthetics score (PES/ WES) will be recorded.

Survival rates.²⁵ The survival rate was defined as the percentage of success implants and remained crowns which never been replaced.

Mechanical complications rates. Veneer chipping, abutments or implants fracture, screw loosening or fracture and other mechanical complications will be recorded during the 1-year

follow-up.

Peri-implant conditions. The indicators of peri-implant conditions included bleeding on probing% (BOP%), pocket probing depth (PD) and modified plaque index (mPI).

Marginal bone loss (MBL).²⁶ Peri-apical radiographs with paralleling technique will be performed on the day of final restorations delivery and 1 year later. The implant length is used as calibration reference. The distance between restoration margin and the most coronal level of implant-bone contact will be recorded. The final result calculate as the mean value of mesial and distal sites. The alteration of the distance between baseline and 1-year follow-up is defined as the MBL.

Pro-inflammatory cytokines in peri-implant crevicular fluid (PICF). The investigators will collect the patients' PICF with the paper strip (PerioPaper Strips; Oraflow Inc., Smithtown, NY, USA) at 1-year follow-up to access differences in pro-inflammatory cytokines (IL-6 and TNF- α) between two groups. Enzyme-linked immunosorbent assay (ELISA) will be used to analyzed PICF and evaluated the concentrations of cytokines. The PICF collection method and cytokines determination referred to Christopher A. Barwacz et al (Figure 2).¹⁸

PES/WES.^{27,28} In this study, pink aesthetic score (PES) and white esthetic score (WES) will be applied for the objective esthetic assessment of the final restoration. The investigators will take patients' intraoral photos by the camera (D70, Nikon, Tokyo, Japan) at 1 year follow up. The aesthetic effect will be assessed by two specific dentists independently. They will asked to give scores for variables of PES (Mesial papilla, distal papilla, level of soft-tissue margin, soft-tissue contour, alveolar process and soft-tissue color and texture) and WES (Tooth form, tooth volume/outline, color, surface texture and transparency) with the 0-1-2 scoring system. Final

PES/WES is the sum of the two.

The primary outcome variable is presupposed to be the success rates. And the null hypothesis is that there is no significant difference regarding mechanical complication rates between two groups.

Statistical analysis

All statistical analyses will be performed using SAS software, version 9.4 (SAS Institute). Normal tests will be performed to know the normality of continuous data before appropriate ways of statistical description and analysis were chosen. Means, standard deviations (SD) and student's t test will be used for data in accordance with normal distribution. Medians, inter quartile range (IQR) and Wilcoxon Rank Sum test will be used for non-normally distributed data. Qualitative data will be described and analyzed by percentage and Chi-square Test. A two-sided *P* value of less than 0.05 will be considered to indicate statistical significance.

Missing data

Sample size calculation was performed accounting for possible loss to follow-up. Moreover, the investigators will account for the data not missing at random due to unbalanced loss to follow-up by handling drop-outs as nonsuccess using the intention-to-treat principle.

Ethical considerations

Ethical approval

All eligible patients will receive study information and informed consent, and any patients who do not sign the consent will not be included in the study.

Withdraw

All patients in this study will be informed that they have the right to withdraw at any time during the study, regardless of whether they withdraw or not, the treatment required by the patients will be accepted.

4. Discussion

There are two main types of zirconia abutments: one-piece monolithic abutments and two-piece hybrid abutments. Choosing the most suitable abutment under different circumstances is one of the important clinical decisions in implant treatment. However, reports on the clinical performance of these two types of abutments remain controversial. To our knowledge, no clinical trials are available now comparing the efficacy of one-piece monolithic abutments and two-piece hybrid abutments used in single implant crowns in esthetic region.

As mentioned above, restorations restored with OPZAs were considered to be accompanied by higher risks of fracture, screw loosening and permanent damage due to stress concentrations, especially with internal implant connections. And restorations restored with TPZAs with friction-fitted titanium inserts seem to require higher machining accuracy and failure of the connection between the zirconia sleeve and titanium insert is a concern.^{21,24-26}

Angulated screw channel system is a novel choice that provide the option of TPZA with a friction-fitted titanium insert. And CAD/CAM zirconia abutment is a general choice of OPZA.

The investigators designed the present study to help evaluate the efficacy of restorations with OPZAs and TPZAs in esthetic region and give clinicians some advice.

5. References

4. van Velzen FJ, Ofec R, Schulten EA, Ten Bruggenkate CM. 10-year survival rate and the incidence of peri-implant disease of 374 titanium dental implants with a SLA surface: a prospective cohort study in 177 fully and partially edentulous patients. *Clin Oral Implants Res.* 2015;26(10):1121-1128.

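### The trial is split-mouth with two implant sites per patient, but the planned rank sum and chi-square tests treat the sites as independent and so give away power

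*Combined protocol and SAP*

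**What the plan says.** The split-mouth label is consistent. The Abstract says "The study is a single center, split-mouth and randomized controlled clinical trial", the Background "the investigators designed this randomized split-mouth clinical trial", and the Overview under 2. METHOD/DESIGN "The present study is designed as a prospective, single-center, split-mouth, randomized controlled clinical trial". The Inclusion criteria call for "patients with two missing teeth in esthetic region and plan to be restored with two single implant crowns".

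The allocation wording is looser. Allocation and blinding says "Eligible patients have two missing teeth, and they will be randomly assigned into two groups", where the pronoun can refer to the patients or to the teeth. The Abstract makes patients the unit assigned: "Eligible patients will be randomly assigned into two groups: OPZAs group (OG) and TPZAs group (TG"). Nowhere is it written that one site in each mouth receives a one-piece abutment (OPZA) and the other a two-piece abutment (TPZA).

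Statistical analysis names Student's t test for normally distributed data (paired or not is unstated), the Wilcoxon rank sum test for other continuous data and the chi-square test for qualitative data, at a two-sided 0.05 level. It names no signed-rank test, McNemar test or model that accounts for the patient.

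The chi-square test therefore covers mechanical complications. The Background says "The primary outcome is prespecified as mechanical complication rates at 1-year follow-up", and section 2, Objectives and Hypothesis, says "The null hypothesis is that there is no significant difference regarding mechanical complication rates between two groups".

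**The concern.** A split-mouth trial asks for two sites per patient so that each patient serves as their own control. Differences between patients in oral hygiene, bite force, smoking and tissue response then cancel out of the comparison. That gain is realised only if the analysis uses the pairing.

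The rank sum and chi-square tests take the two sets of sites as unrelated samples. When sites in the same mouth are alike, these tests use a standard error that is too large. P values come out too big, and confidence intervals built the same way come out too wide. A real difference between abutment types is then more likely to be missed, including on the outcome that the null hypothesis concerns. A statistician who followed the section as written would run an analysis that does not fit the design, even if allocation had been done exactly as intended.

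**Working it through.** **Inputs.** From the documents: two sites per patient, the tests named, two-sided alpha of 0.05. The documents give no sample size, event rate, standard deviation or within-patient correlation, so there is no planned figure to reproduce. Assumed here: within-patient correlation r = 0.1, 0.3 or 0.5; 80% power for the paired test as the reference; 30 patients for binary outcomes.

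**Continuous outcomes, one site per abutment type in each of n patients, common variance s².**

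1. The true variance of the difference in means is 2(1−r)s²/n. An unpaired test uses 2s²/n.
2. The nominal critical value of 1.96 therefore acts as c = 1.96/√(1−r) = 2.066, 2.343, 2.772.
3. True type I error = 2[1−Φ(c)].
4. Power when a paired test has 80% = 1−Φ(c−2.802), where 2.802 = 1.960+0.842. The arguments are −0.736, −0.459 and −0.030.
5. Relative number of patients needed to restore 80% with the unpaired test = [(c+0.842)/2.802]².

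| | r = 0.1 | r = 0.3 | r = 0.5 |
|---|---|---|---|
| True type I error | 3.9% | 1.9% | 0.6% |
| Power (paired test: 80%) | 77% | 68% | 51% |
| Patients needed, relative | 1.08 | 1.29 | 1.66 |

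Simulation with 30 patients agrees: type I error is 3.9%, 1.9% and 0.7% for the unpaired t test, and 3.9%, 2.0% and 0.8% for the rank sum test.

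**Binary outcomes, 30 patients.** The probability that both sites have an event is p11 = p1p2 + r√[p1(1−p1)p2(1−p2)]. For example, at 30% v 10% and r = 0.3, p11 = 0.03 + 0.3 × 0.1375 = 0.071, so the discordant probabilities are 0.229 and 0.029. Enumerating all possible tables, with chi-square uncorrected, gives:

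| Values at r = 0.1 / 0.3 / 0.5 | Chi-square | Asymptotic McNemar | Mid-p McNemar | Exact McNemar |
|---|---|---|---|---|
| Type I error, 5% event rate | 2.1 / 1.0 / 0.3% | 2.3 / 1.4 / 0.6% | 0.6 / 0.3 / 0.1% | 0.1% or less |
| Type I error, 10% event rate | 4.3 / 2.2 / 0.8% | 4.8 / 4.1 / 2.6% | 2.4 / 1.5 / 0.6% | 0.8 / 0.4 / 0.1% |
| Power, 30% v 10% | 50 / 50 / 49% | 50 / 63 / 86% | 50 / 59 / 74% | 39 / 46 / 57% |
| Power, 10% v 2% (r = 0.1 / 0.3 only) | 20 / 17% | 21 / 22% | 10 / 9% | 4 / 3% |

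For 10% v 2%, r = 0.5 is impossible: p11 cannot exceed 0.02, so r is at most (0.02−0.002)/√(0.09×0.0196) = 0.43. For 30% v 10%, r = 0.5 is close to its own maximum, so the 86% is a best case.

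Pairing therefore helps when events are common and sites are clearly correlated. With rare events asymptotic McNemar gains only about 1 to 4 points over chi-square, and the mid-p and exact versions do worse than chi-square.

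**If whole patients were allocated and implants analysed as independent.** The error reverses: type I error = 2[1−Φ(1.96/√(1+r))] = 6.2%, 8.6%, 11.0% for continuous outcomes. For binary outcomes (15 patients, 30 implants per arm) it is 6.6%, 9.0%, 11.6% at a 10% event rate. At a 2% rate it is 0.6%, 1.1%, 1.8%, which is no inflation.

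**The case against.** The strongest reply is that split-mouth ordinarily means both treatments in one mouth. The label recurs throughout, the two-site rule fits it, and mentioning two missing teeth in an allocation paragraph makes most sense if the sites are what is divided. This stands. The loose allocation text is mainly a matter of wording.

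A reader might infer from the Abstract that whole patients are allocated, so that false positives are inflated to about 11%. The documents do not support that as the likely reading. It would require staff to disregard the label, so it serves only as a reason to clarify.

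A reader might also infer from the February 2019 start in the Overview that patients were allocated before version 2.0 of December 2020. The cover page gives 2020/12 to 2022/12, so earlier allocation cannot be presumed. That date conflict is a separate matter to reconcile.

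Two further points stand. Student's t test may have been meant as paired, so the continuous figures apply to it only if it is run unpaired; they apply to the rank sum test in any case. And the loss is small at r = 0.1 or with rare events; the 30% v 10% example is favourable to the paired test.

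What remains is that two of the three named tests do not fit the stated design, and one of them is the test for the outcome in the null hypothesis.

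**Conclusion.** The analysis section is wrong as written for a split-mouth trial. The rank sum and chi-square tests ignore the pairing, and the t test is left unspecified. With positively correlated sites the result is conservative tests and lost power, not extra false positives.

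The size rests wholly on assumptions. For continuous outcomes the loss from 80% power runs from about 3 points at r = 0.1 to about 29 points at r = 0.5. For binary outcomes with 30 patients it runs from almost nothing to 37 points across the cases computed, and it is a few points at most in the rare-event case (10% v 2%). At a 5% event rate much of the conservatism comes from sparse data, and a change of test will not cure it.

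This should still be settled before any analysis, because the test has to match the unit of randomisation and the correction costs almost nothing.

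**What to change.** 1. In Statistical analysis, specify the paired t test for normally distributed within-patient differences, the Wilcoxon signed-rank test otherwise, and the asymptotic McNemar test as the main test for binary outcomes. Keep exact or mid-p McNemar as sensitivity checks only, since with few events both are more conservative than the chi-square test they would replace.
2. Report each paired difference with its confidence interval, and state that power is low if mechanical complications are rare.
3. As a supporting clarification, reword the Abstract and Allocation and blinding along these lines: within each patient, the two sites are randomly allocated, one to an OPZA and the other to a TPZA. Define OG and TG as groups of sites.
4. If any patients were in fact allocated as whole patients, record this and analyse with clustering by patient.

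The cost is a few sentences and minor analysis work. No extra patients or visits are needed.

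### The plan provides no masking for the two dentists who score PES/WES; scoring coded 1-year photographs would be a cheap improvement to this non-primary outcome

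*Combined protocol and SAP*

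**What the plan says.** The Allocation and blinding subsection of METHOD/DESIGN is brief on masking: "The study is an open-label trial without blinding". It names no role to which this does not apply.

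The PES/WES paragraph under Outcomes first says that the investigators will take "intraoral photos by the camera (D70, Nikon, Tokyo, Japan) at 1 year follow up". It then says: "The aesthetic effect will be assessed by two specific dentists independently". The dentists rate a list of soft-tissue and crown features, such as contour, color, texture and transparency, "with the 0-1-2 scoring system". The paragraph does not mention coded images, viewing order or the raters' knowledge of the abutment.

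The trial is split-mouth. The inclusion criteria call for "patients with two missing teeth in esthetic region and plan to be restored with two single implant crowns".

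**The concern.** PES/WES is the only esthetic outcome listed, in a trial set in the esthetic region, and it depends wholly on what a rater decides. The protocol presents it as an objective assessment, but the one safeguard described is that two people score separately. That protects each rater from the other's opinion. It does not protect either from knowing which abutment is being scored.

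If the raters know the allocation, the reported esthetic difference between one-piece and two-piece abutments could partly reflect what they expected to see. Neither the randomization nor the planned tests (t test or rank-sum test, two-sided 0.05) would detect or remove that.

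**Working it through.** The plan states no figure on this point, so there is none to reproduce. The check sets the relevant statements side by side.

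1. **Is any role exempt from the open-label statement?** Allocation and blinding declares no blinding. The Overview, Recruitment, Outcomes, Statistical analysis, Missing data and Discussion text contains no exception, masked reading or coded images. None is exempt.

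2. **Does independent scoring supply masking?** No. It describes the raters' relation to each other, not to the allocation.

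3. **How could knowledge of the abutment enter the result?** Let Δ be the true mean difference in PES/WES between abutments. Let b₁ and b₂ be the average shifts in score that raters give to one-piece and two-piece sites because they know the type. The expected observed difference is then Δ + (b₁ − b₂).
   - Randomization balances the sites, so it protects Δ. It does not act on b₁ − b₂.
   - Within-patient comparison removes patient effects. It does not remove b₁ − b₂, which differs by abutment within the patient.
   - Combining two raters leaves whatever part of b₁ − b₂ they share.
   - Successful masking makes b₁ − b₂ zero in expectation, because the rater cannot tell the sites apart by type.

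4. **Can b₁ − b₂ be sized or signed?** No. The documents give no PES/WES standard deviation, expected difference or number of patients, and they do not predict which abutment will look better.

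5. **Does it reach the primary comparison?** The Background says: "The primary outcome is prespecified as mechanical complication rates at 1-year follow-up". The objectives section says: "The null hypothesis is that there is no significant difference regarding mechanical complication rates between two groups". The end of Outcomes names success rates as primary instead. PES/WES is the primary outcome under neither statement.

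6. **Is masked scoring feasible with what is planned?** Photographs at 1 year and two raters are already in the plan. The text implies, without saying so, that the scores are read from the photographs. If they are, masking needs no extra visit, rater or patient procedure, and does not change sample size or alpha.

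7. **Does the split-mouth design matter?** Reading it as one site per abutment in each patient, a rater who identifies one site also knows the other. Both sites may appear in one image, so cropping or framing matters as well as coding.

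8. **Could photographs already exist?** The Overview gives Feb. 2019 for the start of the clinical component. The title page gives 2020/12 as the start, and version 2.0 is dated 2020/12/10. If the earlier date is right, 22 months separate it from the version date. A crown delivered in the first 22 − 12 = 10 months could then have had its 1-year photograph. Such images can be coded but not reframed, only cropped.

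**The case against.** The strongest reply is that open-label conduct is openly declared, so this is a design choice and not a contradiction. That stands. But an open-label treatment phase does not require unmasked reading of photographs, and the protocol gives no reason for leaving these two raters unmasked.

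A second reply is that the mechanism rests on silence. The documents do not say that the raters will be told the allocation, or that they treated the patients. The text has the investigators take the photographs and two designated dentists give the scores, which may mean the raters are not the operators. This also stands: a reader might infer that the raters will know each site's abutment, and the documents do not establish it. What they establish is that the plan permits it. If the raters are in fact masked, the blanket statement is inaccurate and the same edit corrects it.

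A third reply is that masking might fail. The Discussion says "Angulated screw channel system is a novel choice that provide the option of TPZA with a friction-fitted titanium insert", and a reader might infer that a screw access opening would reveal the two-piece abutment. That is speculative, since the documents do not say how crowns are retained or what a photograph would show. It supports hiding identifying features where possible and no more.

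Finally, the chairside, radiographic and laboratory measures fall under the same open-label statement. That is true. This point is confined to PES/WES because the planned photographs and raters offer a ready remedy there. It does not imply that masking is present or impossible elsewhere.

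**Conclusion.** The point holds as a cheap improvement to one non-primary outcome. As written, the plan allows PES/WES to be scored with knowledge of the abutment, and a better method is available from material already planned.

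The size is unknown and no direction is claimed. Three stronger conclusions might be inferred, and the documents support none of them:

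- **That the primary result is biased.** PES/WES is not primary under either statement. This assumes that the success rate, which the protocol does not define separately, contains no esthetic threshold; nothing in the text suggests one.
- **That one abutment is favored.** The documents do not predict which will look better.
- **That the many item scores per patient measure the problem.** A count of ratings says how often judgement is exercised, not how far a total score would move.

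The conclusion also assumes that PES/WES is read from the 1-year photographs, which the protocol should state outright.

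**What to change.** Keep the open-label sentence and add an exception to it. Replacing the sentence would leave the blinding status of chairside examiners, radiograph readers and laboratory staff unstated. Suggested addition:

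> except that the two dentists scoring PES/WES will score from the 1-year intraoral photographs without knowledge of the allocation; images are coded, presented in random order, and cropped or framed where possible to hide features that identify the abutment while keeping the tissue and teeth needed for scoring; the code is held by an existing staff member who does not score and is released only after scores are locked.

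Photographs already taken but not yet scored can be coded in the same way, with cropping in place of prospective framing. The report should state whether either rater treated the patients.

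**Cost:** a little image preparation and code keeping by existing staff, with the same two raters and no added visit. The protocol gives no sample size. Assuming 10 to 40 patients with one view per site, the work is 2 × 10 = 20 to 2 × 40 = 80 images; more views per site multiply this. That the cost is small is a judgement, not a documented figure. **Downside:** masking may be incomplete if a rater recognizes a case or a feature, though partial masking still improves on none.
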